**Existing Approved Registry** 

8.0 Select appropriate funding sources for this study:

Name Internally Funded Support

Other Funding Sources:

Note: If the funding source of the study is 'Industry Funded Support', Clinical Research Administration (CRA) will be notified.

If your study requires CRA review, please upload applicable documents, including sponsor protocol, drug brochure, etc: Name Version LMA vs Spinal F&A Nursing Support Letter 0.01

Help Help CRP Information

1.0 The proposal should be submitted to the appropriate Clinical Review Panel (CRP) for scientific review. If you are unsure of which Clinical Review Panel to select, please contact [name] at [contact] \* Name Anesthesiology

Help

Date: Wednesday, January 18, 2017 10:33:58 AM

Prin

t Close ID: 2016-0499 Section: PART I - Study Identification Information

Н

# elp Regulatory Status of Drugs and Devices

1.0 The regulatory status of the drugs or devices in this research

proposal is: Name Does not apply to this study

Help Help Pharmacy Involvement / Impact to EPIC

1.0

Is this an inpatient study?

Yes No

2.0 \* Will this study have Investigational Drug Service involvement?

(Pharmacy will be purchasing/dispensing any medications being used and/or study requires placebo and patient randomization)

Yes No

3.0

If the answer to either question is yes, please explain briefly below AND contact [name] at [contact] ([contact]) or [name] at [contact] ([contact]).

## Help

https://ecap.hss.edu/eCAP/ResourceAdministration/Project/PrintSmartForms?Project=com.webridge.entity.Entity%5BOID%5B7 E7099039664F74FA0FE0FE7... 3/36

Date: Wednesday, January 18, 2017 10:33:58 AM

Prin

t Close ID: 2016-0499 Section: PART I - Study Identification Information

Η

# elp Study Locations

1.0 Select the Research Facilities where this study will be

conducted: Facility HSS

- 1.1 If Other, please specify:
- 2.0 \* Is this a multi-Center study?

No

ID: 2016-0499 Section: PART II - Clinical Research Proposal - Nature of Study This section will be reviewed by the appropriate Clinical Review Panel. Each of the headings in this section must be addressed.

Η

# elp Specific Aims or Research Questions

1.0 What is the condition or intervention to be studied?

General anesthesia with laryngeal mask airway (LMA) versus spinal anesthesia for foot and ankle surgery, with both groups receiving sciatic nerve blockade in the popliteal fossa plus adductor canal ('saphenous') block.

https://ecap.hss.edu/eCAP/ResourceAdministration/Project/PrintSmartForms?Project=com.webridge.entity.Entity%5BOID%5B7E7099039664F74FA0FE0FE7... 4/36

Please click Here for example.

2.0 What is/are the research question(s)/specific aim(s)? Pose

very specific questions that can be addressed within the proposed design of the study. Prioritize them in order of importance.

- 1) Does general anesthesia with LMA decrease time until PACU discharge compared with spinal anesthesia (when both groups receive popliteal plus adductor canal blocks)?
- 2) Is there a difference in post-operative pain, nausea, discomfort and needs or opioid consumption with LMA versus spinal anesthesia on top of blocks?
- 3) Is there a difference in satisfaction from anesthesia with LMA versus spinal anesthesia on top of blocks?
- 3.0 What is/are the hypothesis(es)?

Our hypothesis is that general anesthesia with LMA with peripheral nerve blocks will be superior in time until PACU discharge (minimum clinically important difference of 45 minutes [Mulroy 2000]) compared to spinal anesthesia with peripheral nerve blocks.

#### References:

Mulroy MF, Larkin KL, Hodgson PS, Helman JD, Pollock JE, Liu SS. A comparison of spinal, epidural, and general

anesthesia for outpatient knee

ID: 2016-0499 arthroscopy. Section: Anesth PART Analg II 2000;91:860-4.

- Clinical Research Proposal - Nature of Study 4.0 Identify and define the primary outcome and when the outcome will be measured. If measuring change in post- operative function is the most important, that will be your primary outcome.

Time from admission to PACU until ready for discharge home (assessed by RA q 15 m)

Criteria used: Modified Aldrete Scoring System (1) and Marshall and Chung Postanesthesia Discharge Scoring System(2)

# Help Help BACKGROUND - Be sure to answer each question individually

#### 1.0 Explain why these research questions are being asked:

Popliteal and adductor canal peripheral nerve blocks (PNBs) provide good pain control for foot and ankle surgery. In the context of the peripheral nerve blocks, spinal anesthesia is typically added to (1) allow surgical use of a thigh tourniquet (2) provide faster onset (and potentially more reliable) surgical anesthesia and (3) ensure patient immobility. However, spinal anesthesia may prolong PACU discharge time and has associated side effects (back pain, headache, TNS – transient neurologic symptoms). General anesthesia also addresses the three concerns discussed previously (tourniquet, reliability, immobility) but when used alone is traditionally associated with higher pain scores, and more nausea. However, the combination of peripheral nerve blocks, general anesthesia (using Laryngeal Mask Airway, LMA), and prophylactic anti-emetics may

https://ecap.hss.edu/eCAP/ResourceAdministration/Project/PrintSmartForms?Project=com.webridge.entity.Entity%5BOID%5B7 E7099039664F74FA0FE0FE7... 5/36

ID: 2016-0499 provide good Section: pain control PART with II - fewer Clinical side Research effects from Proposal the general - Nature anesthesia, of Study and hasten the

discharge home as compared to spinal.

2.0 What is the background of the topic that you believe is important for the reviewer to know in considering this protocol, including prior studies by this research team. Describe strengths and deficiencies of prior studies; explain how this study fits in. Include references.

Peripheral nerve blocks (PNBs) have increased in popularity due to their efficacy and safety in providing postoperative analgesia by reducing pain, opioid consumption and side effects (1,2). PNBs are often combined with general anesthesia, or neuraxial anesthesia. It is not clear which of these accompaniments most improves the patient experience. When feasible, neuraxial anesthesia is often preferred over general anesthesia because of association with better perioperative outcomes (3). Neuraxial anesthesia may have fewer side effects, such as post-operative nausea and vomiting (PONV)(4) and confusion (5). Spinal anesthesia has advantages over general anesthesia in terms of pain, functional recovery and side effects for ambulatory lower limb surgery, in the absence of peripheral nerve blocks (PNB)(6,7). However, the presumed advantages of neuraxial anesthesia (minimized opioids, improved analgesia and reduced nausea) may possibly also be achieved by combining PNBs with general anesthesia.

The previous non-randomized pilot study applied PNBs plus antiemetic prophylaxis and an opioid sparing protocol among foot and ankle patients (receiving spinal anesthesia plus blocks) and TSA patients (receiving general anesthesia or sedation plus blocks). Results showed low rates of nausea in all groups and no incidence of emesis in any groups. However, no previous studies have compared LMA general anesthesia to spinal anesthesia in the presence of a double block (popliteal + adductor canal) in terms of time to discharge home, satisfaction, severity of pain and PONV, and opioid consumption and side effects in an ambulatory foot and ankle population.

3.0 Identify specific gaps in current knowledge that this study is intended to

fill.

This study will compare LMA general anesthesia to spinal anesthesia on top of popliteal plus adductor canal blocks for foot and ankle surgery in terms of discharge time, satisfaction and side effects, which has not been done before.

 $https://ecap.hss.edu/eCAP/ResourceAdministration/Project/PrintSmartForms? Project=com. webridge.entity. Entity \%5BOID \%5B7E7099039664F74FA0FE0FE7...\ 6/36$ 

ID: 2016-0499 Section: PART II - Clinical Research Proposal - Nature of Study

4.0 How will answering these questions change clinical practice, change concepts about the topic or confirm the work of other investigators?

There is a possibility that in the setting of a double block for foot and ankle surgery, general anesthesia can shorten time to discharge without increasing side effects, compared to spinal anesthesia. This will hopefully lead to more investigative work on general anesthesia with nerve blocks vs spinal anesthesia with nerve blocks that might change the preference of clinicians when deciding upon the best anesthetic regimen for foot and ankle patients.

5.0 Is this a pilot study that could lead to a more definitive protocol or different study? Yes No

5.1 If you answered No, please explain below:

This study is comparing two standard of care protocols and will provide information regarding the effectiveness of each. Therefore, this study will not lead to a more definitive protocol or different study.

6.0 Please upload reference or additional document here (if needed).

Name Description There are no items to display

#### Help

https://ecap.hss.edu/eCAP/ResourceAdministration/Project/PrintSmartForms?Project=com.webridge.entity.Entity%5BOID%5B7 E7099039664F74FA0FE0FE7... 7/36

ID: 2016-0499 Section: PART II - Clinical Research Proposal - Nature of Study

Н

# elp Study Design

1.0

#### Observational:

Name Description There are no items to display

2.0

# Experimental:

Name Description

Randomized Controlled Clinical Trial

 $https://ecap.hss.edu/eCAP/ResourceAdministration/Project/PrintSmartForms? Project=com. webridge.entity. Entity \%5BOID \%5B7E7099039664F74FA0FE0FE7...\ 8/36$ 

This is the "gold standard" for clinical research. These prospective studies have at least two groups. Patients meeting strict inclusion/exclusion criteria are enrolled and randomly assigned to receive either an experimental intervention or to receive what is considered to be an acceptable alternative – usually the current standard of care or a placebo (e.g., study of hylauronic acid injection versus cortisone for arthritis).

- 2.1 If Other, please specify:
- 2.2 If Randomized Controlled Clinical Trial is selected, please choose one of the following: Name Other

If other, please list name or indicate N/A below:

Standard of care general anesthesia with LMA and spinal anesthesia with popliteal and adductor canal nerve blocks ID: 2016-0499 Section: PART II - Clinical Research Proposal - Recruitment & Enrollment

Н

# elp Recruitment

1.0

Check all that apply to describe your study population:

**Population Patients** 

Vulnerable Populations There are no items to display

- 1.1 If Other, please specify:
- 2.0 Inclusion Criteria: list characteristics that potential subjects and

controls need to have. Use a bullet format, if applicable.

18-75 aged patients

ID: 2016-0499 ASA1-3

Section: PART II - Clinical Research Proposal - Recruitment & Enrollment Elective foot and ankle day surgery procedures, lasting between 1 and 3 hours as per surgeon, performed by 3 co-investigator surgeons. planned for combined popliteal and adductor canal block no contraindications for spinal or LMA general anesthesia

3.0

Exclusion Criteria: list characteristics that would cause you to exclude potential subjects and controls.

Justify any age, ethnicity, language, or gender-based exclusion criteria. Use a bullet format, if applicable.

Incapable of providing informed consent, contraindications for regional or LMA anesthesia (anticoagulation, infection at injection site) anticipated difficult airway, BMI>40, anticipated surgical procedure time less than 1 hour or more than 3 hours, Hx of severe PONV ASA >3, peripheral neuropathy affecting the operative extremity pregnant or nursing women, chronic opioid use (daily use of opioids one month prior to surgery/ patients requiring chronic pain interventions) prone position OSA with planned admission overnight to the hospital known allergy/sensitivity to any study medications planned admission after surgery Non-English speaking

4.0 Age Range: 18-75

5.0 Describe how you will identify and recruit potential subjects

for participation in the study.

Surgeon co-investigators will introduce the concept of the study to patients during a preoperative office visit. Potential patients will be identified on the schedule the day before surgery and approached in the holding area of the Hand and Foot Surgery Center, where informed consent will be obtained by a study staff working in conjunction with an attending physician participating in the study. Approximately 2-6 patients per week will be enrolled.

6.0 \* Please select enrollment type from following drop down list:

Over Course of Study

#### Help

 $https://ecap.hss.edu/eCAP/ResourceAdministration/Project/PrintSmartForms? Project=com. webridge.entity. Entity \%5BOID \%5B7E7099039664F74FA0FE0FE7...\ 9/36$ 

ID: 2016-0499 Section: PART II - Clinical Research Proposal - Recruitment & Enrollment

Н

# elp Patients

1.0 Please check the box(es) below that best reflect how patients will be identifed and recruited for participation.

How subjects will be identified Potential subjects will be identified after a review of medical records of patients under the care of one or more of the study investigators Medical records and/or other Institution sources (databases,registries,billing records,pathology reports,admission logs) will be reviewed to identify potential participants. May involve access of records by individuals not involved in the patient's care. Potential subjects will be identified by their treating physicians and referred to the researchers. Patients' private and identifiable information will not be shared prior to receiving permission from the patient to do so. Potential subjects will be identified from a registry of individuals interested in research opportunities. Subjects will roll-over from another research study.

Potential subjects will self-refer in response to advertisements.

Н

# elp Target Enrollment

- 1.0 \* What is the maximum number of subject you plan to enroll in this study at HSS?(Please enter a number) 36
- 2.0 If this is a multi-center study, indicate the projected total subject accrual across all sites.

Н

Н

elp ID: 2016-0499 Section: PART II - Clinical Research Proposal - Interventions or Observations

# elp Interventions and Observations

1.0

Be specific and describe the Interventions or Observations that will be part of this research project. Include a detailed description of the treatment arms, if applicable.

Patients will be randomized into either the Spinal/Block Group or General Anesthesia/Block Group. The randomization will be performed by a research staff member not otherwise involved in the project. The patient and research staff performing assessments/administering questionnaires will be blinded to the group assignment.

#### Intraop-protocol:

Spinal/Block Group: Ultrasound (US) guided sciatic nerve blocks in the popliteal fossa and adductor canal block with 25 mL and 10 mL, respectively, of 0.25% bupivacaine (plus 2 mg preservative-free (PF) dexamethasone / 30 ml), performed under procedural IV sedation protocol. IV sedation protocol: midazolam, 2-5 mg IV + Glycopyrrolate, 0.1 mg IV + Ketamine, 10-20 mg, + propofol as needed. Spinal protocol: 45-60 mg 1.5% mepivacaine, depending on the expected case duration (45 mg for cases with projected duration 1-2 hours, 60 mg

https://ecap.hss.edu/eCAP/ResourceAdministration/Project/PrintSmartForms?Project=com.webridge.entity.Entity%5BOID%5B7 E7099039664F74FA0FE0FE... 10/36

ID: 2016-0499 for cases with Section: projected PART duration II - Clinical 2-3 hours). Research Intraoperative Proposal - sedation Interventions maintained or Observations with propofol infusion and

ketamine, 10 mg/hr (in addition to the 10-20 mg given for block sedation).

General Anesthesia/Block Group. Blocks performed as above. General anesthesia protocol: After induction with propofol and insertion of the LMA, anesthesia maintained with titrated propofol infusion, sevoflurane, ketamine 10 mg/hr (in addition to the 10-20 mg given for block sedation).

Both groups will receive IV ondansetron (4 mg), famotidine (20 mg), dexamethasone (4 mg in addition to block dexamethasone) and ketorolac 30 mg (unless age>75 or weight<60 kg, then 15 mg).

#### Post-op instructions:

Opioids will not be administered intraoperatively until emergence from sedation (Spinal/Block Group) or from general anesthesia (General Anesthesia/Block group). Tourniquet-related stimuli (being transient in nature) will be addressed with propofol and ketamine (and sevoflurane in general anesthesia group). If patients appear to have surgical pain on emergence, IV hydromorphone will be given as needed (in 0.5 mg increments).

Standardized post-op pain protocol:

Narcotic of choice (Percocet, Norco, Oxycodone, Dilaudid, etc.) with a quantity of 60 pills DVT PPX of choice (aspirin, xarelto, lovenox, etc) Ibuprofen 200mg, take 3 tablets TID for a total of 3 days (quantity 27 pills) Zofran 4mg PO q12h prn nausea for a 2 day supply (quantity 4 pills) No prescribed lyrica or gabapentin to patients enrolled

#### Collection of outcomes:

Demographics and baseline information (NRS pain, PONV, PQRS Cognitive Domain, backache and headache history, medication consumption, Leiden Discomfort and Needs) will be obtained in the holding area before surgery.

After anesthesia end time, readiness for PACU discharge will be assessed every 15 minutes using the modified Aldrete scoring system. Once the modified Aldrete criteria is met, the patient will be assessed every 15 minutes using the Postanesthesia Discharge Scoring System, which will be used to determine final readiness for PACU discharge time. PACU nurses and physical therapists will assess and instruct the patient with the knowledge of whether the patient received general or spinal anesthesia, but they will be asked not to reveal to the patient which treatment he/she received.

1 hour and 2 hours after PACU admission (or when ready for discharge), NRS pain, PONV, PQRS Cognitive Domain, and Leiden Discomfort and Needs will be assessed. Popliteal and adductor canal blocks will be assessed using an alcohol swab when either spinal wears off or sufficiently awakened from GA. When readiness for PACU discharge is met, ORSDS and blinding assessment will be administered.

On POD 1, patients will be contacted by phone to collect NRS pain, PONV, PQRS Cognitive Domain, Backache/TNS and Headache/PDPH, medication consumption, ORSDS and Leiden questionnaire outcomes, as well as "If you need similar surgery in the future, would you request the same anesthetic that you received this time? (Yes/No)". If TNS or PDPH is identified, patients will be followed up for duration of symptoms.

Study-Specific Procedures

Day Who?

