# PACU, 1 hour after admission PACU, 2 hours after admission PACU, ready for

# POD 1 discharge

Identify eligible patients on schedule day before surgery. Confirm length of surgery.

RA X

Obtain consent

Anes MD/ Surgeon

X

Assess readiness for PACU Discharge (q15

RA X (if not met) X (if not met) X (if not met)

1/18/2017 Print: 2016-0499 - Spinal versus General Anesthesia with Popliteal and Adductor Canal Blocks for Ambulatory Foot and Ankle Surgery. A Double-Blinded... ID: 2016-0499 min until criteria Section: met) PART II - Clinical Research Proposal - Interventions or Observations NRS pain, PONV, PQRS Cognitive RA Domain XXX (if not ready for discharge) ХХ Backache/TNS Headache/PDPH and RA X X Collect opioid and non-opioid consumption 2.0 Will you be collecting human fluid or tissue? Yes No If yes, what will you be collecting? Fluid Tissue (Intraoperative and/or outpatient collection) Help Help Data Collection 1.0 Indicate what data will be collected. Variable Time point(s) Data Source Who Collects? Demographics: DOB, MRN, Race, Ethnicity, BMI, Gender, Phone number https://ecap.hss.edu/eCAP/ResourceAdministration/Project/PrintSmartForms?Project=com.webridge.entity.Entity%5BOID%5B7 E7099039664F74FA0FE0FE... 12/36 RA X X (for PACU duration) X ORSDS RAXX Leiden Perioperative care Patient Satisfaction questionnaire (LPPSq) RA X Leiden Discomfort and Needs RA X X X (if not ready for discharge) XXBlock assessment RA X X (when spinal wears off or (Baseline awakened from reading) GA)

Blinding Assessment RA X

Pre-op Medical Record Research Assistant Comorbidities, Risk factors associated with outcomes Pre-op Medical Record Research Assistant

ID: 2016-0499 Randomization/Group Section: PART assignment II - Clinical Pre-op Research Proposal - Interventions Randomization or Observations scheme

Research Assistant created by staff member not involved in project

ASA, Type of anesthesia, induction time, anesthesia start & end time, difficult spinal/general, TQ time

https://ecap.hss.edu/eCAP/ResourceAdministration/Project/PrintSmartForms?Project=com.webridge.entity.Entity%5BOID%5B7 E7099039664F74FA0FE0FE... 13/36

Intra-op Anesthesia Record Research Assistant

Type of surgery, surgery start & end time

Intra-op Medical Record Research Assistant

Time from PACU admission to readiness for PACU discharge

Patient: Aldrete score (Aldrete JA. The post- anesthesia recovery score revisited. J Clin PACU, every 15 minutes

Anesth 1995) and after anesthesia end time

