**PACU** 

Medical (yes/no)

record: Incidence

Research Assistant

Blinding assessment PACU Patient Research Assistant

Block assessment Pre-op, PACU Patient Research Assistant

Unexpected adverse events, including ICU admission

Intra-op to POD 1 Medical Record Research Assistant

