#### 4.0 Please state who will insure that the Randomization is carried out and if

#### anyone will be blinded to the Randomization group:

The primary investigator and co-investigators will ensure that randomization is carried out. The research assistants administering surveys/questionnaires and patients will be blinded.

elp ID: 2016-0499 Section: PART II - Clinical Research Proposal - Sample Size & Data Analysis

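### The research assistant who scores the primary endpoint is declared blinded, but the block-test cue and a non-disclosure request limited to the patient can reveal the arm before readiness is recorded

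*Combined protocol and SAP*

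**What the plan says.** Interventions and Observations 1.0 states: "The patient and research staff performing assessments/administering questionnaires will be blinded to the group assignment". Randomization 4.0 repeats it: "The research assistants administering surveys/questionnaires and patients will be blinded". The registry title calls the trial double-blinded. The primary outcome (Specific Aims 4.0) is time from PACU admission to readiness for discharge home, scored by the research assistant every 15 minutes on two named scales.

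The procedures that bear on this are:

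- **Block test.** Under Collection of outcomes: "Popliteal and adductor canal blocks will be assessed using an alcohol swab when either spinal wears off or sufficiently awakened from GA". The Study-Specific Procedures schedule gives the test to the research assistant with the same cue, and the Data Collection table agrees: "Block assessment Pre-op, PACU Patient Research Assistant".
- **PACU staff.** Nurses and physical therapists work knowing the anesthetic, and "they will be asked not to reveal to the patient which treatment he/she received". The research assistant is not mentioned.
- **Data table.** One row lists "ASA, Type of anesthesia, induction time, anesthesia start & end time, difficult spinal/general, TQ time", with time point, source and collector given as "Intra-op Anesthesia Record Research Assistant". The group-assignment row, broken in the extracted text, also names the research assistant: "Research Assistant created by staff member not involved in project".

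A check of blinding in both patient and research assistant is planned with the Bang index (Specific Aims 5.0; Data Analysis 3.0).

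**The concern.** The hypothesis is directional: LMA patients are expected to be ready sooner. The person who decides at each 15-minute check whether the criteria are met should therefore not know the arm, and the plan relies on blinding for this. A cue worded as one event for spinal patients and another for general-anesthesia patients has to be applied by someone who knows which event to wait for. Colleagues who know the arm work beside the scorer and have been asked to keep it from someone else. If either route discloses the arm before readiness is recorded, expectation can enter the primary endpoint. The planned Bang index would measure such a failure but would not prevent it.

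**Working it through.** **1. The block test and the endpoint.** The same role does both. Collection of outcomes ties the ORSDS and the blinding assessment to the moment readiness is met, but gives the block test only its arm-specific cue. In that section the block test is described before the assessments made at readiness. Assessment of Research Procedures 1.0 suggests that waiting for the spinal to resolve can delay discharge. If so, in the spinal arm the cue would tend to come before readiness is recorded. That is an inference, because the schedule cannot confirm it: the block row shows a pre-operative baseline mark and one PACU mark, and the column of the PACU mark is lost in the extracted text.

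**2. Non-disclosure.** The plan recognises that PACU staff could disclose the arm and addresses this for the patient. The general statements that assessors are blinded set the aim, but no instruction to these staff covers the research assistant.

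**3. Data table (supporting only).** It names a role, not a person. Its time-point column shows when a variable arises, not when it is abstracted. No passage assigns the task to a different person or makes it wait until after scoring.

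**4. The plan's own sample size.** Inputs from Sample Size and Data Analysis 2.0: difference 45 minutes, SD 42, alpha 0.05 (taken as two-sided), power 80%. The exact two-sample t-test needs 14.70, so 15 per arm. Dividing by the Wilcoxon relative efficiency of 0.955 gives 14.70 / 0.955 = 15.39, so 16, the stated figure. Then 32 × 1.10 = 35.2, so 36. This point does not alter the sample size. Power at the stated inputs is 83.5% with 16 per arm and 87.7% with 18.

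**5. Illustration of sensitivity.** The documents give no size for scoring bias, so this is an assumption, not an estimate or a bound. Suppose a share f of one arm is recorded one 15-minute step late and there is no true difference. The mean shift is d = 15f minutes. The standard error is 42 × √(2/18) = 14.0 minutes at 18 per arm and 42 × √(2/16) = 14.8 at 16. The chance that the two-sided t-test gives p < 0.05 (noncentral t) is:

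| f | d (min) | d / 45 | 18 per arm | 16 per arm |
|---|---|---|---|---|
| 1/3 | 5 | 11% | 6.4% | 6.2% |
| 1/2 | 7.5 | 17% | 8.2% | 7.8% |
| 2/3 | 10 | 22% | 10.7% | 10.0% |
| 1 | 15 | 33% | 18.0% | 16.5% |

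Reaching 10% needs a shift of about 9.4 minutes at 18 per arm (9.4 / 15 = 63% of one arm) or 10.0 minutes at 16 per arm (67%). A simulation with times rounded up to a 15-minute grid agrees to within about 0.3 percentage points.

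**The case against.** The strongest reply has five parts.

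- **The scorer need not know the arm.** The block-test sentence is passive. A nurse who knows the arm could call the research assistant when the test is due, and the lost schedule column could be the ready-for-discharge one. Both are possible, so a reader should not infer that the test is scheduled before readiness. But the readable text neither provides for such a call nor ties the test to readiness, and the timing of a call could itself hint at the arm.
- **The cue has a purpose.** The lay abstract says a spinal numbs the body below the waist, so a block test done before it resolves could not be read. This stands. It rules out simply testing both arms at one early time, but not testing after readiness is recorded.
- **Spinal recovery is visible anyway.** This also stands. Some exposure is inherent, and how much the two procedures add to it is not known.
- **The data-table rows prove nothing about timing.** Correct. A reader might infer from the pre-operative time point that the scorer holds the allocation before surgery. The documents do not support that: the table names a role, Randomization 4.0 speaks of research assistants in the plural, and the uploaded collection forms, which might set an order, are not available here.
- **Safeguards exist.** Two named scales limit discretion. The opaque envelopes conceal allocation, but they do not blind the scorer in the PACU.

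**Conclusion.** The point holds as a gap between the declared blinding and two procedures that, followed as written, can reveal the arm to the endpoint scorer before readiness is recorded. The data-table rows support it but would not carry it alone. A reader might go further and infer that the scorer will be unblinded, that the double-blind label is false, or that the error rate is inflated to some figure in the table. The documents support none of these: another person could give the cue, the scheduled position of the test is unreadable, and the illustration rests on an assumed one-directional scoring error. On that assumption a small leak matters little, and only a broad one, about two-thirds of an arm moved by a full step, doubles the error rate. The reason to act is that this part of the exposure is avoidable at almost no cost. It should be fixed, with medium confidence, and the size of the gain is unknown.

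**What to change.** 1. Have the research assistant do the PACU block test only after the readiness time is recorded, in both arms. If an earlier reading is wanted, have staff who know the arm and do not score readiness take it.
2. Extend the non-disclosure request to PACU nurses and physical therapists so that it covers the assessing research assistant as well as the patient.
3. State in the Data Collection table that group assignment and anesthesia-record fields that reveal the technique are abstracted only after that research assistant's readiness score is recorded, and preferably after the POD 1 outcomes.
4. As a clerical tidy-up, align the blinding-assessment row, which lists only the patient as source, with the planned assessment of both patient and research assistant.

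The cost is a few sentences of protocol text and a reordered collection sheet. The downside is a later block reading and later abstraction of a few fields. The sample size and the analysis do not change.
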